This study is a randomized open label clinical trial that will compare the safety and efficacy of pyronaridine-artesunate and artemether-lumefantrine in the treatment of malaria among children aged 3 to 144 months who have microscopically confirmed symptomatic *Plasmodium falciparum* malaria. The study will be carried out at the Oni Memorial Children's Hospital, [name]. One hundred and sixty-two children between 3 and 144 months who meet the inclusion criteria will be enrolled after obtaining written or witnessed signed informed consent from the parents or guardian. Details obtained from the enrolee will be entered into a case record form specifically designed for the purpose of accurate documentation. A detailed history and physical examination will be carried out on each enrolee. Finger prick blood samples will be taken from each enrolee for thick blood smear for malaria parasite, haematocrit and blood spots on filter paper. Five millilitres of venous blood will be taken from an arm vein for baseline liver function tests, creatinine and random blood glucose on days 0, 3, 7 and 28.

Enrolees will be randomized into one of two groups. Group one will receive pyronaridine-artesunate while group two will receive artemether-lumefantrine at standard doses. Enrolees will be seen daily from days 0-3, and on days 7, 14, 21 and 28. Study drugs will be administered supervised at standard dosage on days 0, 1, and 2. History taking, physical examination and blood smears will be done at each contact time. Special attention will be paid to adverse effects.

Parasite clearance time, fever clearance time and cure rates will be compared between the two groups. The data collected from the participants will be entered into Epi info version 6 databases and then transferred to SPSS Statistics Software version 20 for statistical analysis.

INTRODUCTION

Background of the study

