attachment)

Where

$Z_{1-\alpha}$ = standard normal deviate for level of significance; at $\alpha=0.05$, it is 1.96

$Z_{1-\beta}$ = standard normal deviate for power (1- β); at $\beta=0.2$ (80% power), it is 0.84 but at $\beta=0.1$ (90%), it is 1.28

P_1 : 28-day cure rate in AL = 96.4%

P_2 : 28-day cure rate in PA = 98.9%

ε : non-inferiority margin= 5%

Applying the formula and parameters above, sample size for each group

90% power: 70 per group [total 140]

80% power: 51 per group [total 102]

Assuming a difference of 2.5% in cure rate between PA and AL (98.9% vs 96.4%) [REF- Roth et al, 2018], 140 patients are required to be 90% sure that the upper limit of a one-sided 95% confidence interval will exclude a difference in favor of the standard group of more than 5%

Total N = 140. Allowing for 20% loss to follow up, the total number of patients required would be 168 to give 84 patients per arm. (See sample size calculation attachment)

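### The enrolment target does not cover the plan's own 20% loss allowance, and it is given as both 168 and 162

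*Combined protocol and SAP*

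**What the plan says.** Section 3.6 (Sample Size Calculation) applies a non-inferiority formula for two proportions with a 5-point margin. Its cure rates are "28-day cure rate in AL = 96.4"% and "28-day cure rate in PA = 98.9"%. The results are given as "90% power: 70 per group [total 140"] and "80% power: 51 per group [total 102"], and the plan adopts the 90% figure of 140. It then adds the allowance for attrition: "Allowing for 20% loss to follow up, the total number of patients required would be 168 to give 84 patients per arm".

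The summary at the front of the document gives a different number: "One hundred and sixty-two children between 3 and 144 months who meet the inclusion criteria will be enrolled". The text supplied does not reconcile the two totals. Section 3.6 refers to a sample size attachment that is not among the documents reviewed.

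**The concern.** There are two separate faults.

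- **Inflation.** An allowance for 20% loss should leave the required number after one in five enrolled children has been lost. Multiplying the evaluable number by 1.20 does not do this, because the loss falls on the enlarged total. The section therefore promises a protection that its figure does not give.
- **Two totals.** The summary and Section 3.6 set different enrolment targets. A reader cannot tell whether recruitment is complete at 162 or at 168.

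At stake are the 90% power claim, under the plan's own loss assumption, and a clear rule for when enrolment ends.

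**Working it through.** **Inputs, from Section 3.6 unless noted.** AL cure rate 0.964; PA cure rate 0.989; margin 0.05; 90% power (deviate 1.28) or 80% (0.84); one-sided 95% confidence limit; 20% loss; equal arms; total 168. The total of 162 is from the opening summary.

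**Step 1: reproduce the evaluable number.**

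- Variance term: 0.964 × 0.036 + 0.989 × 0.011 = 0.034704 + 0.010879 = 0.045583.
- Distance to the margin: 0.05 − (0.964 − 0.989) = 0.075, and 0.075² = 0.005625.
- Formula: n per arm = (Zα + Zβ)² × 0.045583 / 0.005625.

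| Zα | 90% power | 80% power |
|---|---|---|
| 1.645 (one-sided 5%) | 69.3, rounds up to 70 | 50.04, rounds up to 51 |
| 1.96 (as printed) | 85.1, rounds up to 86 | 63.5, rounds up to 64 |

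The plan's 70 and 51 follow from 1.645. They do not follow from the 1.96 printed in the list of symbols.

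**Step 2: reproduce the enrolment total.**

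- 140 × 1.20 = 168, which is the plan's figure.
- 140 / (1 − 0.20) = 175, or 88 per arm = 176 with equal arms. Check: 176 × 0.80 = 140.8.
- 162 / 140 = 1.157, so 162 matches neither form of a 20% allowance.

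**Step 3: what each total leaves, and the loss it covers.**

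| Enrolled | Left after 20% loss | Per arm | Loss that still leaves 140 |
|---|---|---|---|
| 168 | 134.4 | 67.2 | 1 − 140/168 = 16.7% |
| 162 | 129.6 | 64.8 | 1 − 140/162 = 13.6% |
| 176 | 140.8 | 70.4 | 1 − 140/176 = 20.5% |

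**Step 4: power by the plan's formula.** Power = Φ(0.075 / √(0.045583/n) − Zα).

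| n per arm | Zα = 1.645 | Zα = 1.96 |
|---|---|---|
| 70 (no shortfall) | 90.2% | 83.6% |
| 67 (168 enrolled, 20% lost) | 89.1% | 82.0% |
| 64.8 (162 enrolled, 20% lost) | 88.2% | 80.7% |

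Reading down a column isolates the effect of attrition: 1.1 to 2.0 points at 1.645, and 1.6 to 2.9 points at 1.96. The gap between the columns comes from the unsettled significance level, which is a separate matter.

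**The case against.** The strongest reply is that the error barely affects the inference. A loss of one to two points of power is within the error of the normal approximation. Enumerating all binomial outcomes, with an unpooled Wald limit at one-sided 5% and the plan's cure rates, gives power of 92.8% at 70 per arm, 93.0% at 67, 93.1% at 65 and 89.6% at 64. On that calculation the 90% claim survives at 67 and at 65. This stands, and it limits the weight of the point. It does not make 168 the right answer to the sum that the plan sets itself, and it does not resolve the conflict between the totals.

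Other objections also have force:

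- The total of 176 holds only if 70 per arm holds. With the printed deviate of 1.96, 86 evaluable per arm are needed, and 86/0.80 = 107.5, so 108 per arm or 216 in all. The level has to be settled first.
- The shortfall assumes that lost children drop out of the primary analysis. The plan defines no analysis set and no rule for missing outcomes. The case record form codes withdrawn and lost children separately from treatment failure and adequate response, so exclusion is a natural reading, but it is not stated.
- Section 3.6 holds the only derivation, so 162 may simply be a slip in the summary. The missing attachment might also explain it. The text should still give one number.
- Describing the allowance as 16.7% would fit the assumption to a number already chosen. It is accurate as a description of what 168 covers, but nothing in the documents supports 16.7% as an expected loss.

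**Conclusion.** The concern holds. Section 3.6 uses the wrong inflation: 168 is 140 × 1.20, whereas 20% loss calls for 175, or 176 with equal arms. The summary's 162 conflicts with it and is unexplained. Under the plan's own loss assumption the arms fall about 3 short (168) or 5 short (162) of the required 70.

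This is a correction the sponsor should make, but it is not a serious loss of power: 89.1% or 88.2% by the plan's formula, against 90.2% at 70 per arm. These figures rest on the plan's cure rates, including the assumed 2.5-point advantage for PA, on one-sided 5%, and on lost children not being counted in the primary analysis.

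**What to change.** 1. Settle the significance level, since the list of symbols prints 1.96 while the calculated sizes and the stated confidence limit are one-sided 5%. The steps below assume that one-sided 5%, and so 70 per arm, is confirmed. If 1.96 is meant, the target must be recalculated from 86 per arm.
2. Use one enrolment total in the summary and in Section 3.6.
3. Choose one of two ways to make the loss statement true:
   - **Keep 168 (84 per arm).** Change 162 to 168 in the summary. Replace the loss sentence in Section 3.6 with wording such as: *With 168 enrolled, 20% loss leaves 67 per arm, giving about 89% power at one-sided 5%.* The plan may add that 140 evaluable children are retained for losses up to 16.7%.
   - **Enrol 176 (88 per arm).** This keeps 140 evaluable at 20% loss.
4. State whether children lost or withdrawn are counted in the primary analysis, so that the meaning of the allowance is clear.

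Cost: if 168 is the working target, the first option is wording only and the second adds 8 children. If recruitment is in fact planned to 162, the options add 6 and 14 children.

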3.6.1 Inclusion criteria

- Individuals of either gender between the ages of 3months (but weight ≥ 5 kg) and 12 years who present with symptoms compatible with acute uncomplicated malaria
- Minimum asexual parasite density of $1000/\mu\text{l}$. This will be done at enrolment for all study participants.
- Fever with an axillary temperature $\geq 37.5^{\circ}\text{C}$ or history of fever within 24hours of presentation
- Residence within 15 kilometers to study site
- Ability to take drugs orally
- Absence of history of ACT intake in the two weeks prior to enrolment
- A signed informed consent from parents or guardian of prospective enrollee to participate in the study

3.6.2 Exclusion criteria

- History of allergy to study drugs i.e. artemisinins, lumefantrine and pyronaridine
- Any concurrent illness that could hamper evaluation of response e.g. bacterial infections, viral infections, severe gastrointestinal disease, malnutrition (weight for height $<70\%$)
- Presence of clinical evidence of severe malaria such as prostration, inability to drink or breast feed, persistent vomiting, convulsion, severe anemia hemoglobin <5 g/dl), unarousable coma
- Patients with known chronic diseases like chronic kidney disease, chronic liver disease, malnutrition, cardiac failure, Sickle Cell haemoglobin (HbSS) etc.
- mixed or mono-infection with another Plasmodium species detected by microscopy;
- presence of severe malnutrition defined as a child aged between 6-60 months whose weight-for-height is below -3 z-score, or has symmetrical edema involving at least the feet or has a mid-upper arm circumference <115 mm)
- Parent or guardian who in the judgment of the investigator will not comply with protocol in the opinion of the investigator

3.7 Sample Collection Procedure

Enrollees who have fulfilled the inclusion criteria would have the details of the study explained thoroughly to them. The parent or guardian will be required to sign an informed consent form once they agree to participate in the study. All enrollees will have a case record form (CRF). The CRF will be used to collect the following details.

1. Socio-demographic, clinical and laboratory details of all enrollees in the study. The CRF will also have the contact information of each enrollee as well as the past medical history.
2. Record details of each visit: These will include clinical details that would be assessed at each clinic visits, including physical examinations, blood film for malaria parasite, and hematocrit values for each enrollee. Any change in contact details or living situation would be noted.

For the enrollees, a medical history will be obtained from parent/guardian including presenting symptoms and current medications. Physical examination will be performed; weight and axillary temperature recorded. A finger prick blood sample will be obtained for thick blood smears and blood spots on filter paper for parasite genotyping. Five milliliters of venous blood sample will also be obtained for assessment of hematological and biochemical parameters.

Blood film for malaria parasite: Thick blood film will be prepared from finger prick sample of each enrollee at each contact time, stained with fresh 10% Giemsa stain at pH 7.2 and read under a light microscope at X1000 magnification. Gametocyte carriage will be specifically looked out for in the thick film on all contact days. Blood spots on filter paper will be obtained at enrollment and at follow up. This will be used for DNA analysis by polymerase chain reaction (PCR) to differentiate re-infection from recrudescence

Blood chemistry and hematology: 5mls of venous blood samples would be taken for clinical chemistry (electrolytes, urea and creatinine as well as a liver function test) evaluation at day 0 and on the follow up days.

Hematocrit measurement: This will be done by the micro-hematocrit method and the result recorded in percentage. The hematocrit will be done at enrolment and at each clinic visit.

3.7.1 Drug administration

Study participants will then be assigned into one of the two treatment groups according to a pre-generated randomization code. Drug treatment will be given in the clinic supervised.

Pyronaridine-artesunate:

Children randomized to group 1 will receive three doses of pyronaridine-artesunate granules or tablets (Pyramax®) manufactured by Shin Poong Pharmaceuticals depending on their body weights. Pyramax® granules comes in sachets with each containing 60mg of pyronaridine/20mg of artesunate while Pyramax tablets contain 180mg pyronaridine/60mg artesunate. Pyramax dosing is once daily for three days. Dosing will be according to the chart below:

| Body weight | No of sachets or Tablets | Regimen |
|--------------|--------------------------|------------------|
| 5 - < 8kg | 1 Sachet | Daily for 3 days |
| 8 - < 15Kg | 2 sachets | Daily for 3 days |
| 15 - < 20 Kg | 3 Sachets | Daily for 3 days |
| 20 - < 24 Kg | 1 Tablet | Daily for 3 days |
| 24 - <45 Kg | 2 Tablets | Daily for 3 days |

Artemether-lumefantrine:

The study participants randomized to group 2 will receive the standard six-dose regimen of artemether-lumefantrine dispersible tablets (Coartem® Novartis pharma) twice daily according to body weights. Each dispersible tablet of Coartem® contains 20mg of artemether/120mg of lumefantrine) and patient will be dosed as follows

| Body weight | No of dispersible Tablets |
|--------------------|----------------------------------|
| 5 -<15 Kg | 1 tablet |
| 15 - < 25 Kg | 2 tablets |
| 25 - <35 Kg | 3 Tablets |
| ≥35 Kg | 4 Tablets |

5 -<15Kg one tablet, 15 - <25 Kg two tablets, 25 - <35 Kg three tablets, and ≥35 Kg four tablets at the following dosing intervals

- 0 hour - 1st dose;
- 8 hours – 2nd dose;
- 24 hours – 3rd dose;
- 36 hours – 4th dose;
- 48 hours – 5th dose
- 60 hours – 6th dose.

The first, third and fifth doses will be administered supervised in the clinic with water (very young children or a glass of milk while the second, fourth and sixth doses will be given by the care-giver at home 8 hours and 12 hours respectively after the first and subsequent morning doses. Mothers will be encouraged to breastfeed very young babies still on the breast soon after drug administration. Parent/guardian will be provided a sachet of milk after consultation on days 0, 1 and 2 for the 2nd, 4th and 6th doses of AL. Parents and care-givers will be also advised to give Coartem™ with a fatty meal e.g. fried plantain or bean porridge (local fatty meals) for the older children especially those who cannot tolerate milk.

Each enrollee will then be observed in the clinic for 1 hour after drug administration for vomiting. If vomiting occurs within 30 minutes of drug administration, the full treatment dose (PA or AL) will be re-administered. If vomiting occurred between 30-60 minutes of drug administration, half the treatment dose will be re-administered. Any enrollee who vomits the repeat dose will be withdrawn from the study and treated with another ACT.

No other antimalarial therapy will be allowed/given throughout the study period (28 days) except there is parasite recurrence. Paracetamol – an antipyretic drug will be administered to study participants with axillary temperatures ≥38.5°C at standard dosage.

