There are limitations to the use of AL which is the commonly used ACT in Nigeria. These include high number of dosing (six) which is not convenient and the need to give the drug with fatty food for optimal absorption of lumefantrine because of its high lipophilic property.[19] Pyronaridine, a Mannich base 1-aza-acridine structurally related to mepacrine and amopyroquine, one of the earliest synthetic antimalarial drugs, was first developed in China over 30 years ago. It has been used as monotherapy in parts of Asia and China.[20] Pyronaridine, is a benzonaphthyridine derivative that is active against *Plasmodium falciparum* and *Plasmodium vivax*.[21, 22]¹⁴

Pyronaridine-Artesunate (PA) is a novel fixed dose ACT drug that received a Positive Opinion through Article 58 from the **European Medicine Agency¹ (EMA)**. This Positive Opinion is a stringent regulatory review and approval granted for a specific group of drugs that will not be marketed in Europe. This rigorous review process is performed in conjunction with the WHO. At the time of the Positive Opinion (registration) PA also obtained WHO prequalification status. Pyramax received approval with EMA for the treatment of acute uncomplicated *P. falciparum* and *P. vivax* malaria. Subsequent EMA approvals have been granted for repeated dosing and for the paediatric formulation of granules in sachets. pyronaridine-artesunate has been found to have good efficacy and tolerability and is cost effective.[23-26] Like DP, pyronaridine-artesunate has a daily dosing regimen and can be taken with or without meals.[23] The studies conducted so far on the efficacy and tolerability of PA showed that other ACTs were not superior to it and there were strong recommendations that PA should be included as a standard antimalarial treatment.[27] The most commonly reported adverse effects were headache, eosinophilia, neutropenia, anaemia, increased platelet count, vomiting, abdominal pain, bradycardia, short lasting transaminase increases and hypoglycaemia.¹⁶ Other studies reported vomiting which may be due to its bitter taste, nausea, loss of appetite and cough.[27] More recent studies provide increasing evidence on the safety of Pyramax.[28, 29]

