3.7.2 Follow-up

Clinical and parasitological evaluation will be done on each day of follow-up or on any other day if the patient feels unwell. Patients will be reminded by phone calls 30minutes before the next dose of AL and on the day before the follow up visit (all enrollees i.e. PA and AL arms) and those who fail to attend follow up will be visited at home. Transportation fare will be given as incentives to the parents or care givers to encourage attendance for follow up. During each visit, a brief clinical history will be obtained to assess new complaints and possible side effects of medications and a physical examination will also be performed. Hematocrit and chemical analysis (bilirubin, blood glucose, creatinine and liver enzymes- AST, ALT & Alkaline Phosphatase) will be done on at enrolment and follow up on days 3, 7 and 28 to monitor possible changes.

Filter paper blood samples for parasite genotyping will be obtained on day 0, 3, 7, 14, 21 and 28 or earlier if enrollee is symptomatic. A finger prick blood sample will be taken to prepare thick blood smears on days 1, 2, 3, 7, 14, 21, 28 and on any other (unscheduled) visit. The slides will be air-dried away from direct sunlight, stained with fresh 10% Giemsa at pH 7.2 for 15 to 20 minutes and read independently by two microscopists. Parasite density (the number of asexual parasites per μl) will be calculated by counting parasites against about 200 leukocytes and assuming a leukocyte count of 8,000/ μl of blood ³⁶. A smear will be considered negative only after screening at least 200 high power fields. However, a slide will be read against 500 leukocytes before it is declared negative. All discordant smears and slides with a parasite density difference $>10\%$ will be read by an independent microscopist and the PI. For quality control 5% of randomly selected slides will be read by an independent microscopist not involved in the study.

Paired samples (D0 and Day of recurrence) of blood spots on filter paper collected from patients with parasite recurrence on or before D28 will be analyzed using PCR techniques for parasite DNA.

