Address (+ brief description):
.....
.....
.....

Symptoms History

Record duration of symptoms in days (Today = 1) Fever: () Vomiting: () Chills & rigors ()

Diarrhoea: () Headache: () Abdominal pains: () Irritability: () Loss of appetite ()

Other complaint 1: Other complaint 2:

Past medical history:

History of drug allergy: (Yes/No) If yes, name of drug:

Any other relevant history 1:

Any other relevant history 2:

Treatment history: Has the child received any of the following drugs in the last 2 weeks (Yes/No)

CQ () SP () PCM () ACT () Specify.....

Antibiotic () Specify..... Other:

Clinical examination:

General: Palor (Yes/No) Icterus (Yes/No) Fever (Yes/No) Dehydration (Yes/No)

CVS: Pulse/min..... Apex Beat..... Heart sounds.....

Respiratory system: Resp. rate..... Breath sound.....

Abdomen: Liver size (Below costal margin)..... Spleen size..... Kidneys.....

Muscle tone: (1) Normal (2) Hypotonia (3) hypertonia Eyes: conjunctivitis/Discharge (Yes/No)

Ears: Discharge (Yes/No)

MP result: PCV.....

**PYRONARIDINE-ARTESUNATE VERSUS ARTEMETHER-
LUMEFANTRINE STUDY**

Study ID- PAAL:

Study ID -----

Study Drug Schedule

| Study Day | Date | Drug [PA or AL] Name of Drug | Dose | Time Drug Given |
|------------------|-------------|---|-------------|------------------------|
| Day 0 | | | 1st | |
| | | | 2nd | |
| Day 1 | | | 1st | |
| | | | 2nd | |
| Day 2 | | | 1st | |
| | | | 2nd | |

Comments:

Any vomiting? Yes/No

Time

Any Redosing?

Time

Any vomiting? Yes/No

Any other comments

CLINICAL FOLLOW UP RECORD

| | D0 | D1 | D2 | D3 | D7 | D14 | D21 | D28 | Day 35 | Day 42 | Other visit |
|---------------------------|-----------|-----------|-----------|-----------|-----------|------------|------------|------------|---------------|---------------|--------------------|
| Date | | | | | | | | | | | |
| Temp (°C) | | | | | | | | | | | |
| Pallor | | | | | | | | | | | |
| Jaundice | | | | | | | | | | | |
| HR/Pulse Rate | | | | | | | | | | | |
| Resp Rate | | | | | | | | | | | |
| Lung Fields | | | | | | | | | | | |
| Liver (cm) | | | | | | | | | | | |
| Spleen (cm) | | | | | | | | | | | |
| Weight (kg) | | | | | | | | | | | |
| PCV (%) | | | | | | | | | | | |
| Parasite Density/ μ L | | | | | | | | | | | |
| Gametocyte Count/ μ L | | | | | | | | | | | |

TREATMENT EMERGENT SIGNS AND SYMPTOMS (TESS)

| Features | Day 0 | | Day 1 | | Day 2 | | Day 3 | | Day 7 | | Day 14 | | Day 21 | | Day 28 | | Day 35 | | Day 42 | | Extra Visit | | Extra Visit | | |

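### Vomiting is watched for after every PA dose but after only half of the AL doses, and the drug-schedule form does not tie vomiting to a dose, so AL vomiting may be under-counted to the extent that carer recall is imperfect

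*Combined protocol and SAP*

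**What the plan says.** Safety is half of the trial's aim (Section 2, Objectives), and the Introduction names vomiting as a reaction to PA: "Other studies reported vomiting which may be due to its bitter taste".

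**Dosing and observation (Section 3.7.1).** For PA, "Pyramax dosing is once daily for three days". AL is the "standard six-dose regimen of artemether-lumefantrine dispersible tablets". The section opens with a general statement, "Drug treatment will be given in the clinic supervised", and the protocol summary likewise describes supervised administration on Days 0, 1 and 2. Later, for AL, Section 3.7.1 says that "the second, fourth and sixth doses will be given by the care-giver at home". The only active check for vomiting is the hour in clinic: "Each enrollee will then be observed in the clinic for 1 hour after drug administration for vomiting".

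**Contact about home doses (Section 3.7.2).** "Patients will be reminded by phone calls 30minutes before the next dose of AL". This call comes before the dose. No check, diary or call after a home dose is described. At every visit, in both arms, staff ask about new complaints and side effects.

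**CRF.** The Study Drug Schedule page has a row for each of two doses on each of three days, with columns for date and time given. Vomiting and re-dosing sit below it in one comment block, "Any vomiting? Yes/No", with Time lines but no dose number or day. The treatment-emergent signs and symptoms (TESS) grid has a Vomiting row, scored for presence and severity by visit day. The Adverse Events Record has columns for Days 0, 3, 7 and 28 and for extra visits, but none for Days 1 and 2.

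**Analysis.** Section 3.7.3 and Data Analysis define no vomiting endpoint, no denominator and no rule on observed doses.

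**The concern.** A by-arm comparison of any vomiting would set PA, where the first hour after every dose is watched by staff, against AL, where that hour is watched for half of the doses and remembered for the rest. Where recall is incomplete, the loss falls on AL, so AL looks better tolerated over a course than it is and PA looks relatively worse.

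The CRF as printed does not let the analyst correct for this later. TESS is scored by visit day, so it cannot separate a morning clinic dose from a later home dose. Vomiting is also a presenting symptom of the illness, which blurs the early entries. The drug-schedule block cannot reliably show which dose was vomited or repeated. If the dose is not recorded when the data are collected, it cannot be recovered afterwards.

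**Working it through.** The plan states no vomiting rate, so there is no figure of its own to reproduce. The dose counts come from Section 3.7.1; everything else is assumed.

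**Coverage by the observation hour.** PA: 3 of 3 doses (100%). AL: 3 of 6 doses (50%).

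**Model.** Let v be the per-dose vomiting risk and r the fraction of home-dose vomiting that is recalled. Assume independent doses and full detection in clinic.

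- PA per course = 1 − (1 − v)³
- AL true = 1 − (1 − v)⁶
- AL recorded = 1 − (1 − v)³(1 − rv)³

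**Equal risk, v = 5%.**

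- PA = 1 − 0.95³ = 14.3%
- AL true = 1 − 0.95⁶ = 26.5%

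| Recall r | AL recorded | Share of affected AL children missed |
|---|---|---|
| 0 | 14.3% | (26.5 − 14.3)/26.5 = 46% |
| 0.5 | 1 − 0.95³ × 0.975³ = 20.5% | 22% (unrounded: 0.0596/0.2649) |
| 1 | 26.5% | 0% |

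**Range of v at r = 0.5.**

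- v = 2%: true 11.4%, recorded 8.7%, missed 24%
- v = 10%: true 46.9%, recorded 37.5%, missed 20%

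**Can the order of the arms reverse?** With different risks p_PA and p_AL, recorded AL falls below PA when r < [1 − (1 − p_PA)/(1 − p_AL)]/p_AL.

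- PA 7%, AL 5%: PA = 1 − 0.93³ = 19.6%; AL true = 26.5%. The threshold is (1 − 0.93/0.95)/0.05 = 0.42. At r = 0 recorded AL is 14.3%, which is reversed. At r = 0.5 it is 20.5%, which is not.
- PA 4%, AL 3%: threshold 0.34.
- PA 6%, AL 4%: threshold 0.52.
- PA 10%, AL 7%: threshold 0.46.
- Equal risks: threshold 0. The gap can shrink to nothing but cannot reverse.

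Reversal therefore needs an AL per-dose risk between about half of the PA risk and just below it, together with low recall.

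**The case against.** The strongest reply is that home-dose vomiting is not left uncollected. AL doses 2, 4 and 6 are due at 8, 36 and 60 hours. With visits nominally at 24, 48 and 72 hours, the carer who gave the dose is seen 16, 12 and 12 hours later, is asked about side effects, and has TESS completed. The Summary of Activities also schedules adverse-event recording on Days 1 and 2. This stands. It makes zero recall an extreme bound rather than an expected case, and it leaves unequal ascertainment rather than absence of capture.

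A reader might infer that the plan will report PA as causing more vomiting when the opposite is true. The documents do not support that. They give no vomiting rates, and the reversal needs the particular combination shown above.

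A reader might also infer that PA vomiting is recorded only when staff see it. That is not so: PA vomiting after the first hour is also collected by recall, with the same items. The imbalance lies in the first hour after the AL home doses.

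Three further points have weight. If vomiting clusters within children, a child who vomits at home is more likely to vomit in clinic too, and the missed share falls. The Time lines might let some events be matched to a dose, and PDF extraction may have altered the page layout. No formal test of vomiting is specified, although a by-arm table is foreseeable given the safety aim.

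**Conclusion.** The concern holds as unequal ascertainment. Staff actively observe 100% of PA doses and 50% of AL doses; the remaining AL doses depend on recall by day, and the drug-schedule block as printed does not name the dose. The likely direction is under-counting of AL. Its size depends on recall: with half of home events recalled, about 20% to 24% of affected AL children would be missed for per-dose risks of 2% to 10%; with complete recall, none. These figures rest on assumed risks, independent doses and full clinic detection. Reversal is a conditional possibility, not a finding. The point bears on the safety comparison only. It is a modest weakness, worth repairing because the repair is cheap and must be in place before data are collected.

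**What to change.** **CRF, Study Drug Schedule.** Replace the single block with one line per dose (PA 1 to 3, AL 1 to 6): place (clinic or home), vomited (yes, no or unknown), re-dosed (yes, no or unknown).

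**Visits on Days 1, 2 and 3.** Ask carers in both arms the same question about vomiting since the last visit. Make sure that the adverse-event page can take Day 1 and Day 2 entries, as the Summary of Activities already expects.

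**Data Analysis.** Report per-course vomiting by arm, labelled as differently ascertained. Add a supplementary table restricted to clinic-observed doses (PA 1 to 3 against AL 1, 3 and 5), with observed doses as the denominator. That table compares the arms like for like per dose, but it leaves out half of the AL exposure, so it should not replace the per-course result.

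**Reminder calls.** The calls before AL doses are an extra contact in one arm. Events volunteered on them should not be held back to even this out, because Sections 3.7.3 and 3.7.4 require prompt reporting of serious events and events of special interest.

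**Text.** Reconcile the protocol summary and the opening of Section 3.7.1, which describe dosing as supervised, with the later statement that three AL doses are given at home. No change to dosing or supervision is asked for.

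The cost is a few more boxes per child, one revised CRF page, two sentences in Data Analysis and one extra table.
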